Appendix B: Vulvovaginal Signs and Symptoms Scale

SIGNS:

To be rated by the investigator during the vulvovaginal examination

Sign	Absent 0	Mild 1	Moderate 2	Severe 3
Edema				
Erythema				
Excoriation or fissures				

Definitions:

Absent: none

Mild: slight

Moderate: definitely noticeable

Severe: marked, intense

SYMPTOMS:

To be rated by the subject

Symptom	Absent 0	Mild 1	Moderate 2	Severe 3
Burning				
Itching				
Irritation				

Definitions:

Absent: I have no discomfort (i.e., burning, itching, irritation)

Mild: I have some discomfort (i.e., burning, itching, irritation), but it does not bother me much

Moderate: I have discomfort (i.e., burning, itching, irritation), which is annoying, but not enough to affect what I am doing

Severe: I have discomfort (i.e., burning, itching, irritation), which is annoying enough to affect what I am doing

PI	Principal Investigator
PP	Per Protocol
PK	Pharmacokinetic
QD	once daily
SD	Standard Deviation
SAE	Serious Adverse Event
SAS	Statistical Analyzing System
SOP	Standard Operating Procedure
TOC	Test of cure
VSS Scale	Vulvovaginal Signs and Symptoms Scale

1. INTRODUCTION

This Statistical Analysis Plan (SAP) is based on the study Protocol Amendment 1 (Version 2.0) dated 13 Jul 2017.

This document provides additional details concerning the statistical analyses outlined in the protocol and reflects any changes to the protocol from any amendments. This plan will not repeat all the definitions given in the protocol but will provide further details of the summaries and analyses planned therein.

2. STUDY OBJECTIVES

Primary Objective:

- To identify the recommended dose of oral SCY-078 in subjects with moderate to severe Acute Vulvovaginal Candidiasis (AVVC) by comparing the efficacy of different dose levels and dosing regimens of oral SCY-078

Secondary Objectives:

- To evaluate the efficacy of oral SCY-078 in subjects with AVVC based on mycological and clinical outcomes
- To evaluate the safety and tolerability of different dose levels and dosing regimens of oral SCY-078 in subjects with AVVC

Exploratory Objectives:

- To explore the efficacy of SCY-078 in subjects with AVVC based on potassium hydroxide (KOH) testing at the TOC visit
- To explore the efficacy of SCY-078 in subjects with AVVC based on additional clinical outcomes
- To explore the prevalence of Candida species among subjects with AVVC
- To explore the in vitro activity of SCY-078 against baseline Candida spp. isolates
- To explore clinical and mycological outcomes by Candida species
- To evaluate the PK of SCY-078 after oral administration of different dose levels and dosing regimens of SCY-078 in subjects with AVVC

3. STUDY DESIGN

This is a multicenter, randomized, double-blind, double-dummy, active-controlled, dose-finding study to compare the efficacy, safety and tolerability of oral SCY-078 compared to oral

fluconazole in adult female subjects 18 years and older with moderate to severe AVVC. Approximately 180 eligible subjects (30 subjects per treatment group) will be enrolled and randomized into the study.

The primary objective of this study is to identify the recommended dose of oral SCY-078 in subjects with moderate to severe AVVC by comparing the efficacy of different dose levels and dosing regimens of SCY-078.

The study will consist of a Screening visit, a Baseline visit on Day 1, a study visit on Day 3 (which will consist of an on-site visit for PK sampling for a subset of subjects and a phone contact for all other subjects), a TOC visit (which will include PK sampling for the PK Subset of subjects) on Day 10 (± 2) and a FU visit on Day 25 (+4). The Screening and Baseline visits may be combined. Efficacy, safety, tolerability and PK assessments will be conducted for the study.

At Screening, subjects who are experiencing vulvovaginal symptoms will be evaluated by the investigator, who will obtain a vaginal sample for local KOH testing and for fungal culture and species identification by the central laboratory. Susceptibility testing will be done at the central laboratory for all positive cultures for *Candida* spp. Additional vaginal samples will be collected, if clinically indicated, to be examined for the presence of other pathogens (e.g., causative agents for bacterial vaginosis, *Trichomonas*, *Herpes* virus, *N. gonorrhoea*, *Chlamydia*, human papillomavirus or other mixed infections) by a qualified laboratory and for the determination of vaginal pH by the investigator. The investigators and the subjects will rate the signs (edema, erythema and excoriation) and symptoms (itching, burning and irritation) of infection, respectively, on a standardized vulvovaginal signs and symptoms scale (the Vulvovaginal Signs and Symptoms [VSS] Scale). Safety procedures, including an abbreviated physical exam, vital signs, laboratory tests and a pregnancy test will also be performed. To be eligible for inclusion, subjects must have a minimum composite score of vulvovaginal signs and symptoms ≥ 7 with at least 2 signs or symptoms having a score of 2 (moderate) or greater in the VSS Scale, a positive KOH test and a normal vaginal pH (≤ 4.5).

At the Baseline visit (which may be combined with the Screening visit), eligible subjects will be randomized in equal allocation (at a 1:1:1:1:1:1 ratio) to one of the following 6 active treatment groups (5 experimental groups and 1 active comparator group):

- Treatment Group 1: oral SCY-078 750 mg QD on Day 1 only
- Treatment Group 2: oral SCY-078 300 mg BID on Day 1 only
- Treatment Group 3: oral SCY-078 450 mg BID on Day 1 only
- Treatment Group 4: oral SCY-078 150 mg BID on Days 1 to 3
- Treatment Group 5: oral SCY-078 300 mg BID on Days 1 to 3
- Treatment Group 6: oral fluconazole 150 mg QD on Day 1 only

Subjects will receive randomized treatment from Day 1 through Day 3. For the purpose of maintaining treatment blinding, all randomized subjects will receive matching SCY-078 placebo

tablets and/or matching fluconazole placebo capsules as needed based on treatment assignment, in a double-dummy fashion. During treatment days, subjects will rate their vulvovaginal symptoms and record dosing details, AEs and concomitant medication use daily on subject diaries. On Day 3, a PK Subset consisting of 10 subjects per treatment group (total of 60 subjects) will visit the site to have PK samples drawn pre-dose (immediately before dosing) and at 2-6 hours' post-dose of either the morning or evening dose. Day 3 will be an on-site visit for PK subjects and a phone contact visit (with a window of +3 days) for non-PK subjects. All subjects (both PK and non-PK subjects) will continue to take their assigned study treatment and rate their symptoms of infection within their subject diaries. Treatment compliance will be reviewed either on site or by phone for all subjects. Study drug may be collected from PK subjects who have completed study drug dosing at the time of this visit.

At the TOC visit (Day 10 [± 2]) vaginal samples will be obtained for local KOH testing and for fungal culture by the central laboratory. In addition, susceptibility testing will be done at the central laboratory for all positive cultures for *Candida* spp. The investigators and the subjects will rate the signs and symptoms of infection, respectively, on the VSS Scale. An abbreviated physical exam, vital sign measurements and safety laboratory tests will also be performed.

Additionally, a single PK sample will be obtained at any convenient time of the day from the PK Subset only. For the PK Subset, the TOC visit must occur as close to Day 10 as possible. All subjects will return their subject diaries. Compliance with study drug dosing will be evaluated and study drug will be collected for all subjects who did not return their study drug on Day 3.

At the FU (Day 25[+4]) visit, vaginal samples will be obtained for local KOH testing and for fungal culture by the central laboratory. In addition, susceptibility testing will be done at the central laboratory for all positive cultures for *Candida* spp. The investigators and the subjects will rate the signs and symptoms of infection, respectively, on the VSS Scale to evaluate clinical outcome.

4. HARDWARE AND SOFTWARE

Statistical analysis will be performed following Novella standard operating procedures and on the Novella computer network. All statistical analysis will be performed using SAS Version 9.3 with program code prepared specifically for the project by qualified Novella statisticians and SAS programmers.

The SAS programs will generate rich-text-formatted (RTF) output with the "RTF" extension using the SAS Output Delivery System (ODS). The summary tables and listings will be formatted using the Times New Roman 9-point font. The RTF output is included in report documents prepared with Microsoft Word and converted to PDF format without typographical change.

Datasets will be created and taken as input to validated SAS programs to generate the report-ready tables, listings, and figures. Each output display will show the names of the data sets and SAS program used to produce it.

5. DATABASE CLOSURE

After completion of all data review procedures, validation of the project database, and approval of the data review document by the study sponsor, the clinical database will be closed and the study will be unblinded. Any change to the clinical database after this time will require written authorization, with explanation, by the Sponsor and the Biostatistician.

6. SAMPLE SIZE DETERMINATION

This is an exploratory study and no formal sample size calculation was performed. Approximately 180 subjects will be enrolled and randomized in an equal allocation (at a 1:1:1:1:1:1 ratio) to the six study treatment groups (see Table 1). Thirty subjects per group are estimated to be adequate to perform an initial assessment of the safety and tolerability as well as the potential efficacy of SCY-078 in subjects with AVVC.

7. ANALYSIS POPULATIONS

The following analysis sets/populations will be used in this trial:

- **Intent-to-Treat (ITT) population:** All randomized subjects
- **Modified Intent-to-Treat (mITT) Population:** All randomized subjects who have a positive KOH test and a confirmed positive mycological culture for yeast at Baseline.
- **Per Protocol (PP) population:** All mITT subjects who have completed the study drug treatment, who have a TOC evaluation AND who have no major protocol deviations (e.g., violation of Inclusion/Exclusion criteria, use of interfering concomitant medications). The TOC evaluation will be considered an evaluation within the Visit 4/ TOC/ Day 10 analysis window and may include unscheduled visits from subjects who attended the TOC visit late. Subjects to be included in the PP population will be determined by the Sponsor/CRO prior to the unblinding of the study. Prior to breaking the blind, additional criteria for exclusion from the PP population may be included to accommodate for unforeseen events that occurred during the conduct of the study.
- **Safety population:** All randomized subjects who received at least one dose of study drug and who have at least one post-Baseline evaluation
- **Pharmacokinetic (PK) population:** All randomized subjects who received study drug and provided at least one PK sample.

The mITT population will be the primary population for efficacy analysis. The ITT and PP population will be secondary for the primary and secondary endpoints only. The Safety population will be used for the analyses of safety endpoints.

All efficacy analyses will be conducted according to the randomized treatment assignment; all safety analyses will be conducted according to the treatment actually received.

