11.2 Exclusion Criteria

A subject will be excluded from participation in the study if she meets any of the following exclusion criteria:

1. Subject has any vaginal condition other than AVVC that may interfere with the diagnosis or evaluation of response to therapy, such as suspected or confirmed concurrent causes of vulvovaginitis and/or cervicitis including bacterial vaginosis, *Trichomonas*, active *Herpes* virus, *N. gonorrhoea*, *Chlamydia*, active human papillomavirus or other mixed infections.
2. Subject requires treatment with the prohibited medications (including prescription and over-the-counter medications, supplements, and herbal products) listed in [Section 21.0 \(Appendix A\)](#), during the following timeframes:
 - a. Systemic and/or topical (vaginal) antifungal treatment, including prescription or over-the-counter products, within 28 days prior to enrollment if administered for the treatment of VVC and during the study for all cases
 - b. CYP3A4/5 inducers and strong time-dependent CYP3A4/5 inhibitors during the 14 days prior to enrollment and during study treatment
 - c. Strong or moderate reversible CYP3A4/5 inhibitors, including azoles and grapefruit juice, during 48 hours prior to enrollment and during study treatment until TOC

- d. Select CYP2C8 substrates during the 48 hours prior to enrollment or during study treatment
 - e. Select P-gp substrates during the 48 hours prior to enrollment or during study treatment SCY-078
3. Subject is actively menstruating at the time of the Baseline visit.
 4. Subject has uncontrolled diabetes mellitus.
 5. Subject has a vaginal sample with pH >4.5.
 6. Subject has a history of or an active cervical/vaginal cancer.
 7. Subject has a known hypersensitivity to SCY-078, fluconazole or any of the components of the formulation.
 8. Subject has a known human immunodeficiency virus infection and/or is receiving chemotherapy or has an illness that, in the judgment of the investigator, is serious enough to induce an immune deficiency.
 9. Subject has had any major illness within 30 days before Screening.
 10. Subject is pregnant or lactating.
 11. Subject has participated in any other investigational study within at least 30 days (or 5.5 half-lives of the investigational product) before signing the ICF.
 12. Subject has received prior treatment with the study drug in a previous trial.

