13.2 Prohibited Medications

Medications specifically not permitted in the exclusion criteria ([Section 11.2](#)) include the following:

- Non-study systemic or topical antifungal therapy
- Topical vaginal corticoids
- Vaginal contraceptives
- Other investigational drug(s)
- Strong CYP3A4/5 inhibitors, select moderate CYP3A4/5 inhibitors, CYP3A4/5 inducers, select CYP2C8 substrates and select P-gp substrates.

See [Section 21.0 \(Appendix A\)](#) for the full list of prohibited medications.

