21.0 Appendices

Appendix A: Prohibited Medications and Medications to be Administered with Caution

Prohibited Medications

The use of any topical vaginal corticoids and contraceptives is prohibited during the study. No antifungal treatment other than the study drug is allowed during the study. In addition, the medications listed below are also prohibited.

Strong CYP3A4/5 inhibitors and CYP3A4/5 inducers

CYP	Strong Inhibitors	Moderate Inhibitors	Inducers ^a
3A4/5	Reversible inhibitors^b 
 • boceprevir • conivaptan • indinavir • itraconazole^c • ketoconazole^c • lopinavir/ritonavir • mibefradil 	Reversible inhibitors^b 
 • fluconazole^c 	
 • avasimibe • carbamazepine • phenytoin • rifampin • St. John's wort
	Time-dependent inhibitors^a 
 • clarithromycin • ritonavir • saquinavir 		

- a. The CYP3A4/5 inducers and strong time-dependent CYP3A4/5 inhibitors listed in this table are not permitted during the 14 days prior to enrollment and during study treatment.
- b. The strong and moderate reversible CYP3A4/5 inhibitors listed in this table are not permitted during the 48 hours prior to enrollment and during study treatment.
- c. No antifungal treatment other than the study drug is allowed during the study.

CYP2C8 substrates

CYP	Substrates
2C8 ^a	amiodarone, amodiaquine, paclitaxel, repaglinide, montelukast, pioglitazone and rosiglitazone,

- a. The CYP2C8 substrates listed in this table are not permitted during the 48 hours prior to enrollment or during study treatment.

P-glycoprotein (P-gp) substrates

P-gp Drug Substrates ^a
digoxin, colchicine

- a. The P-gp substrates listed in this table are not permitted during the 48 hours prior to enrollment or during study treatment

Medications to be administered with Caution and Monitored as Appropriate

CYP	Moderate Inhibitors
3A4/5	Reversible inhibitors^a 
 • amprenavir • aprepitant • atazanavir • buprenorphine • ciprofloxacin • crizotinib • cyclosporine 
 • darunavir/ritonavir • fosamprenavir • imatinib • grapefruit juice, blood oranges, mulberry juice
	Time-dependent inhibitors: 
 • diltiazem • erythromycin • verapamil

CYP3A4 substrates

CYP	Substrates

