11.8 Efficacy Endpoints

11.8.1 Primary Efficacy Endpoint

The primary efficacy endpoint is the percentage of subjects with Clinical Cure at the TOC visit.

Clinical Cure is defined as complete resolution of signs and symptoms of vulvovaginal infection without need for further antifungal treatment. Specifically, for complete resolution, any sign or symptom should be absent (score = 0) by the TOC visit. If any sign or symptom is missing, the subject's Clinical Cure status will be considered as missing.

Conversely, Clinical Failure is defined as no response to therapy or incomplete resolution of signs and symptoms or need for additional vulvovaginal or systemic antifungal therapy. If the subject receives or self-administers topical drug therapy for the treatment of vulvovaginal irritation/pruritus such as topical analgesic or corticosteroid after completing treatment with the study drug and before the TOC visit, the subject is considered a clinical failure.

The signs (edema, erythema and excoriation or fissures) and symptoms (itching, burning and irritation) of infection will be assessed by the investigator and the subject, respectively, on the VSS Scale. The VSS Scale is a standardized, predefined scale where each sign and symptom will

be given a numerical rating based on severity (absent = 0; mild = 1; moderate = 2; severe = 3) to calculate a total composite score.

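### The Per-Protocol rule, read naturally, removes subjects whom the endpoint itself defines as clinical failures, and that can only raise PP cure rates

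*SAP*

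**What the plan says.** **PP membership.** SAP Section 7 admits to PP those mITT subjects who completed study drug, have a TOC evaluation, and "who have no major protocol deviations (e.g., violation of Inclusion/Exclusion criteria, use of interfering concomitant medications". The Sponsor/CRO settles membership before unblinding and may add exclusion criteria up to that point. *Interfering* is not defined.

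**Prohibited medication.** Protocol Section 13.2 lists "Non-study systemic or topical antifungal therapy" and "Topical vaginal corticoids". Appendix A repeats both bans and states: "No antifungal treatment other than the study drug is allowed during the study". Exclusion criterion 2a in Protocol Section 11.2 covers antifungals "within 28 days prior to enrollment if administered for the treatment of VVC and during the study for all cases". An antifungal taken after randomization could therefore fall under either of the two deviation examples in SAP Section 7.

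**Endpoint.** SAP Section 11.8.1, like Protocol Section 18.7.1, counts as Clinical Failure "incomplete resolution of signs and symptoms or need for additional vulvovaginal or systemic antifungal therapy". For treatment of vulvovaginal irritation or pruritus it adds a topical limb: "topical analgesic or corticosteroid after completing treatment with the study drug and before the TOC visit, the subject is considered a clinical failure".

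**Role of PP.** mITT is the primary efficacy population. ITT and PP are secondary for the primary and secondary endpoints. SAP Section 11.9.3 analyses the exploratory endpoints in mITT and PP only.

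**The concern.** A subject who takes an antifungal before TOC because study drug has not worked has had an outcome, and Section 11.8.1 records it as one. The same act is use of a prohibited drug, which is the obvious candidate for an interfering concomitant medication. Nothing in either document separates medication taken because treatment failed from medication taken for some other reason, and nothing keeps the first group in PP as failures.

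Exclusion would then depend on a post-randomization outcome. Deciding membership blind does not help, because the selection works through the outcome and needs no knowledge of the arm. The study aims to identify a dose by comparing regimens, with about 30 subjects randomized per arm. At that size a few deleted failures move a displayed cure rate by several points.

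**Working it through.** **Which events overlap**

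| Medication before TOC | Prohibited? | Clinical Failure under SAP 11.8.1? |
|---|---|---|
| Additional vulvovaginal or systemic antifungal | Yes (Protocol 11.2, 13.2, Appendix A) | Yes |
| Topical vaginal corticosteroid for irritation/pruritus | Yes (Protocol 13.2, Appendix A) | Yes, after study drug is completed |
| Topical analgesic for irritation/pruritus | Not listed | Yes, after study drug is completed |

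The overlap is firm in the first two rows. In the third it exists only if *interfering* is read to cover a permitted drug.

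**Effect of removing these failures.** The plan states no cure rate, rate of such treatment or PP rate, so there is no figure of its own to reproduce. Every p and f below is an assumption.

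Let p be an arm's cure rate with all failures kept, and f the share of its failures that take such medication before TOC and are dropped, with no other exclusions.

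- PP rate = p / [1 − (1 − p)f]. For 0 < p < 1 and f > 0 the denominator is below 1, so the PP rate exceeds p.
- PP odds = [p/(1 − p)] / (1 − f). The odds ratio for arm A against arm B is therefore multiplied by (1 − f_B)/(1 − f_A), and is unchanged when f_A = f_B.

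*One arm.* p = 0.50 and f = 5/15: 0.50 / (1 − 0.50 × 1/3) = 0.60. In counts, 15/25 = 60.0% against 15/30 = 50.0%, a rise of 10.0 points.

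*Range for one arm*, rise in percentage points:

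| p | f = 0.1 | f = 0.3 | f = 0.5 |
|---|---|---|---|
| 0.5 | 2.6 | 8.8 | 16.7 |
| 0.7 | 2.2 | 6.9 | 12.4 |
| 0.8 | 1.6 | 5.1 | 8.9 |

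*Two arms.* With all failures kept, take 21/30 (70%) against 15/30 (50%): difference 20.0 points, odds ratio (21/9)/(15/15) = 2.33.

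| Failures dropped | PP rates | Difference | Odds ratio |
|---|---|---|---|
| Equal shares: 3 of 9 and 5 of 15 | 21/27 = 77.8%, 15/25 = 60.0% | 17.8 points | (21/6)/(15/10) = 2.33 |
| Higher share in weaker arm: 3 of 9 and 8 of 15 | 21/27 = 77.8%, 15/22 = 68.2% | 9.6 points | (21/6)/(15/7) = 1.63 |
| Higher share in stronger arm: f = 0.5 and f = 0.1 | 0.70/0.85 = 82.4%, 0.50/0.95 = 52.6% | 29.7 points | 2.33 × 0.9/0.5 = 4.20 |

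The cure rates rise in every row. The difference shrinks in the first two and grows in the third. The odds ratio, which is the SAP's pairwise measure (Section 11.9.1), is unchanged, falls and rises in turn.

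**Is the weakest arm inflated most?** With equal f, relative inflation is 1/[1 − (1 − p)f], which grows as p falls: at f = 0.3 it is 1.06 at p = 0.8, 1.18 at 0.5 and 1.27 at 0.3. Absolute inflation peaks at p = 1 − [1 − √(1 − f)]/f, which is 0.49, 0.46 and 0.41 for f = 0.1, 0.3 and 0.5, and is smaller below the peak: at f = 0.3 it is 8.8 points at p = 0.5 but 8.0 at p = 0.3. With unequal f the order can reverse, as in the last row above: 12.4 points in the stronger arm against 2.6 in the weaker.

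**The case against.** The strongest reply is that exclusion is inferred. SAP Section 7 removes *major* deviations, offers examples rather than a list, and leaves the decision to blinded review, which could keep these subjects as failures under the present wording. That stands: removal is the natural reading, not a stated rule. But a rule that allows a failure to be either counted or deleted has not been pre-specified.

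The second reply is that little depends on it. mITT is primary, neither mITT nor ITT excludes anyone for medication, PP is secondary, the study is exploratory and not powered for formal comparisons, and dropping users of interfering medication is ordinary PP practice. The points about role and power stand, and they limit the importance. The appeal to ordinary practice does not cover a case in which the medication use is part of the endpoint.

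A reader might also infer that PP inflates the weakest arms most and so flatters weak doses. The documents do not support this. They give no rate of such treatment by arm, and the working shows that the result depends on the scale and on how f varies. Illustrations that assume a higher share of treated failures in the weaker arm build in the compression that they then show.

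**Conclusion.** The point holds as a defect of the secondary PP analysis. The natural reading of SAP Section 7 removes subjects who meet the Clinical Failure definition through a prohibited antifungal or topical corticosteroid before TOC. If it is applied that way, PP clinical cure rates can only rise. Risk differences generally change, and odds ratios change when the share of failures treated differs by arm. The direction of the between-arm distortion is not fixed.

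The size is unknown. Over the assumed range of p from 50% to 80% and f from 0.1 to 0.5, one arm's rate rises by 1.6 to 16.7 points.

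Three stronger readings should not be drawn. The documents do not say that these subjects will be excluded. They do not list topical analgesics as prohibited, so that limb is weaker. And they do not put the primary comparison at risk: these subjects stay in mITT as failures, and nothing says that the dose will be chosen on PP.

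**What to change.** Before unblinding, add to SAP Section 7:

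*Subjects who meet the Clinical Failure definition in Section 11.8.1 because of antifungal or topical therapy before TOC are not excluded from the PP population for that medication use; they remain in PP and are counted as failures for clinical cure and the composite endpoint.*

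The text should point to the definition and timing in Section 11.8.1 and not restate them. The topical limb applies only after study drug is completed, and looser wording, such as *after first dose*, would widen the primary endpoint.

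The same addition should say how these subjects count for:

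- mycological eradication, since a negative culture after a non-study antifungal cannot be credited to study drug;
- the follow-up endpoints, which Section 11.9.2 also analyses in PP.

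The other PP criteria stay as they are, and medication that does not trigger Clinical Failure remains a matter for blinded review.

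The cost is a short SAP edit and no new data. PP cure rates become slightly less favourable. In the one-arm example, PP returns from 15/25 = 60% to 15/30 = 50%, so this source of bias in clinical cure is removed.
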